# 7.9 Changes in the planned analysis

The following changes have been included, compared to the protocol [1]:

- In the secondary endpoint on SANDE, the global score has been included (section 3.2.2) in addition to severity and frequency scores.
- A clarification on the use of data from blinded reading center and site investigator has been added in section 7.8.
- The first key secondary endpoint in section 10.2.1 has been reworded in alignment with the definition of the Schirmer I test primary endpoint.
- A clarification on the use of a Mixed Model for Repeated Measurements (MMRM), extension of ANCOVA for repeated measurements, after imputation through MI-RD for IDEEL, NEI scale and TFBUT endpoints has been added in section 10.2.2, in alignment with treatment policy estimand used for primary endpoints.
- Considering the progress of data collection, the overview of planned statistical analyses (section 6.2) has been updated compared to protocol. A single database lock will be performed at the end of the study (instead of two locks), followed by the release of the KFR and by the final analyses. This decision represents a conservative choice in favor of the integrity of the study.

# 7.10 Blind Data Review Meeting (BDRM)

BDRMs will be held before DB locks. Any other details will be provided in the BDRM documentation (Pre-Analysis Review).

# 7.11 Software

All statistical analyses and data processing will be performed using Statistical Analysis Systems (SAS®) Software (release 9.4 or later).

# 8. Evaluation of Demographic and Baseline Characteristics

# 8.1 Subject enrolment and disposition

All presentations of subject disposition will be by treatment group, and overall.

For describing the subject disposition, the following populations will be summarized:

- 1. Subjects screened overall (N).
- 2. Subjects enrolled overall (N, 100%).
- 3. Subjects enrolled but not randomized and reasons for non-allocation overall (N, %).
- 4. Subjects randomized by treatment group, and overall (N, %).
- 5. Subjects randomized but not treated by treatment group, and overall (N, %).
- 6. Subjects in each analysis set (FAS, SAF, PP) and reasons for exclusion by treatment group, and overall (N, %).

For points 1 - 3, the percentage denominator will be the number of ENR subjects; for points 4 - 6, the percentage denominator will be the number of randomized subjects within each arm.

Listings will be provided based on ENR set.

# 8.2 **Protocol deviations**

All the protocol deviations will be discussed case by case before unblinding of the treatment code with the clinical team during the BDRM and described in the BDRM Report. Any deviation from these protocol procedures will be reported in the study-specific Protocol Deviation form.

Number of occurrences and of subjects with at least one major and minor protocol deviation will be summarized for each treatment and overall.

# 8.3 Study discontinuations

The following information will be summarized for the randomized patients by treatment and overall:

- Trial completers.
- Subjects who discontinued the trial prematurely (and reasons).
- Number of subjects who completed each planned visit.
- Subjects who discontinued the IMP (and reasons).
- Subjects who discontinued the IMP but completed the study.

- Subjects who discontinued the IMP and discontinued the trial prematurely.
- Broken randomization code (and reasons).

If more than 30% of randomized subjects discontinue the study prematurely, the distribution of the time from randomization to discontinuation will be summarized using the Kaplan-Meier method. The degree of uncertainty will be expressed with 95% confidence limits (calculated per the method proposed by Greenwood). Comparison of curves among arms will be performed with the log-rank test. Kaplan-Meier graphs will be presented along with the number of patient-at-risk at exact time points. Subjects who have not prematurely discontinued the trial will be censored at study termination.

# 8.4 Demographics and baseline characteristics

The baseline demographic characteristics will be summarized by treatment and overall, by means of descriptive statistics. No statistical testing will be carried out.

The following demographic and baseline characteristics will be reported:

- Geographic region of the site (Europe, US),
- Site,
- Age (years),
- Sex (Male, Female),
- Race,
- Ethnicity,
- Potential childbearing,
- Contraception method,
- Pregnancy test performed and result and reasons for no pregnancy test.

Potential childbearing, Contraception methods, and Pregnancy test results will be provided for female patients only.

#### 8.5 Ocular and systemic Medical History and Concomitant Diseases

A disease is defined:

- "Previous disease" if it is not ongoing at screening visit ("ongoing" box is ticked as "No").
- "Concomitant disease" if it is ongoing at screening visit ("ongoing" box is ticked as "Yes").

Previous and/or concomitant diseases will be coded using Medical Dictionary for regulatory activities (MedDRA) dictionary and reported in separate tabulations. Frequency distributions and percentages will be summarized by treatment, type (Ophthalmic and Non-Ophthalmic), by System Organ Class (SOC) and Preferred Term (PT).

Counts will be given for both SOC and PT by subject. Subjects experiencing more than one previous/concomitant disease event will be counted only once within each SOC and PT.

Subjects experiencing more than one disease classified in the same category will be counted only once.

#### 8.6 **Prior and concomitant medications**

A medication is defined:

- "Prior medication" if taken and stopped prior to first dose of study treatment.
- "Concomitant medication" if taken after the first dose of study treatment.

according to the available parts of the medication dates (see Table 7). In case of missing information not directly allowing allocation to either of the two above categories of medications, the medication will be considered as concomitant.

Prior and/or concomitant medications will be coded using World Health Organization Drug Dictionary and reported in separate tabulations. Frequency distributions and percentages will be summarized by treatment, type (Ophthalmic and Non-Ophthalmic), by Anatomical Main Group (1st level of the Anatomical Therapeutic Chemical (ATC) classification), Chemical Subgroup (4th level of the ATC classification) and Preferred Name.

Subjects taking more than one medication classified in the same category will be counted only once.

# 8.7 Dry Eye History

The dry eye history characteristics will be summarized by treatment and overall, by means of descriptive statistics. No statistical testing will be carried out. The following information will be reported:

- Eye affected by Dry Eye.
- Time since first diagnosis of Dry Eye.
- Has the patient received prior treatment for dry eye?
- Eye diagnosed with Severe Sjögren's Dry Eye.
- Time since first diagnosis of Severe Sjögren's Dry Eye.

# 8.8 Other baseline characteristics

No statistical testing will be carried out for comparing baseline characteristics.

#### 8.8.1 Eligible eye

Eye which is defined as eligible eye will be reported.

#### 8.8.2 SANDE

Baseline SANDE scores (frequency, severity, and overall) will be descriptively summarized by treatment and overall as a continuous variable. Information on the SANDE assessment (done/not done) will be reported, with reasons in case of not execution. Rules for derivation of SANDE scores are reported in section 12.2.

#### 8.8.3 IDEEL

Baseline IDEEL scores will be descriptively summarized by treatment and overall as a continuous variable. Information on the IDEEL assessment (done/not done) will be reported, with reasons in case of not execution. Rules for derivation of IDEEL scores are reported in section 12.3.

## 8.8.4 BCDVA

Baseline SNELLEN equivalent scores will be summarized by treatment and overall as an ordinal variable for the right eye, the left eye and eligible eye. Information on the BCDVA assessment (done/not done) will be reported, with reasons in case of not execution.

# 8.8.5 External ocular examination

The results of the external ocular examination will be summarized by treatment and overall, by means of descriptive statistics. Information on the assessment (done/not done) will be reported, with reasons in case of not execution. The following information will be reported for the eligible eye:

- Any clinically significant abnormalities and types.
- Any evidence of punctual occlusion.
  - $\circ$  if yes, by what mechanism was this seen.
- Any clinically significant abnormalities in the function of the eyelid muscles.
  - if yes, specification.
- Any abnormalities in the conjunctiva and types.

The same information will be provided, in a separate tabulation, for the non-eligible eye.

### 8.8.6 Schirmer test I and Schirmer test II

Baseline Schirmer test I and Schirmer test II will be descriptively summarized by treatment and overall as continuous variables. Information on the assessments (done/not done) will be reported, with reasons in case of not execution.

# 8.8.7 Slit Lamp Ophthalmic Exam

The results of the Slit Lamp Ophthalmic Exam will be summarized by treatment and overall, by means of descriptive statistics. Information on the assessment (done/not done) will be reported, with reasons in case of not execution. The following information will be reported for the eligible eye:

- Evaluation.
  - if Abnormal, comments.
- Horizontal diameter of the cornea (mm).

# 8.8.8 Fluorescein Staining (NEI Scale)

The results of the Fluorescein Staining will be summarized by treatment and overall, by means of descriptive statistics. Information on the assessment (done/not done) will be reported, with reasons in case of not execution. The following information will be reported for the eligible eye:

- Has Ocular surface staining performed?
- Cornea Result.
- Conjunctiva Result.
- Total Cornea Score.
- Total Conjunctiva Score.
- NEI Score

Rules for derivation of NEI scores are reported in section 12.4.

# 8.8.9 Tear Film Break-up Time (TFBUT)

Baseline TFBUT results will be summarized by treatment and overall as a continuous variable for the right eye, the left eye and eligible eye. Information on the TFBUT assessment (done/not done) will be reported, with reasons in case of not execution.

# 9. Evaluation of Treatment Compliance and Exposure

# 9.1 Compliance to IMP

The assessment of patients' compliance to the IMP will be made by determining the number of drops administered to the eligible eye. On a per patient basis, the evaluation of the compliance will be done using the following formula:

 $Compliance (\%) = \frac{\text{total number of drops in the eligible eye taken during the treatment period}}{\text{total number of drops in the eligible eye scheduled during the treatment period}} \times 100$ 

Where derivations rules for "total number of drops in the eligible eye taken during the treatment period" and for "total number of drops in the eligible eye scheduled during the treatment period" are provided in Table 3.

Compliance will be summarized by treatment and overall, by means of summary statistics. In addition, compliance to IMP will also be presented for the following categories: <80%, 80%-120\%, >120%.

#### 9.2 Exposure to IMP

The extent of exposure to IMP in days will be summarized with descriptive statistics by treatment group and overall. The extent of exposure (days) will be calculated using the formula reported in Table 3.

#### 9.3 Use of preservative free artificial tears

The use (n° drops/day) of preservative free artificial tears will be summarized with descriptive statistics by treatment group and overall, by study period (treatment / follow-up) and overall according to the following formulas:

$$Use_{TREAT} = \frac{total \ number \ of \ drops \ of \ the \ preservative \ free \ artificial \ tears \ during \ the \ treatment \ period}{total \ number \ of \ days \ of \ the \ treatment \ period} \times 100$$

$$Use_{F-UP} = \frac{total \ number \ of \ drops \ of \ the \ preservative \ free \ artificial \ tears \ during \ the \ follow - \ up \ period}{total \ number \ of \ days \ of \ the \ follow - \ up \ period} \times 100$$

Details are provided in Table 3.

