## 5.6. CONCOMITANT MEDICATION

As a general rule, in addition to the standard chronic treatment with topical CsA (or other ophthalmic treatment of the same class) that will not be discontinued to participate in the study, no ophthalmic medication other than study drug will be given to the patient from the screening day until all of the final study evaluations have been completed, except for preservative free artificial tears provided by the Sponsor.

IMP should be administered first and concomitant medications should be administered as follows:

- Topical CsA eye drops (or other topical ophthalmic treatment of the same class) as previously prescribed at least 15 minutes apart
- Preservative free artificial tears provided by the Sponsor at least 15 minutes apart

The preservative free artificial tears will be provided by the Sponsor and can be used according to the following scheme:

- 1) During the 4 weeks of masked treatment, only if strictly needed, the patient will instill one drop in both eyes.
- 2) During the 8 weeks of Follow-up period post-treatment one drop will be instilled in both eyes TID (morning, afternoon and evening).

The use (n° drops/day) of preservative free artificial tears will be clearly documented in the patient's diary and eCRF.

All medications (including over-the-counter drugs, herbal products, vitamins, and antacids) taken within 4 weeks prior to the start of and throughout the study will be clearly documented on the Concomitant Medications eCRF page.

Medication entries should be specific to product name (if a combination drug product) and spelled correctly. The dose, unit, frequency, route of administration, start date, discontinuation date, and indication should also be recorded. For medications administered only one time, the frequency column may reflect "once."

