| Total number of drops in the
eligible eye scheduled during the
treatment period             | 3*(Date of End of Treatment visit – Date of Randomization + 1) – (assessments not done on Randomization visit + assessments not done on End of Treatment visit)  |
|---|--|
| The extent of exposure (days)   | Date of last administration of IMP – Date of first administration of IMP + 1   |
| Total number of drops of the
preservative free artificial tears
during the treatment period | Sum of Morning/Afternoon/Evening Number of drops taken for eligible eye between Randomization visit date and End of Treatment date.
(from the eCRF form "Frequency of preservative free artificial tears use" forms)  |
| Total number of days of the treatment period  | End of Treatment date – Randomization date + 1   |
| Total number of drops of the
preservative free artificial tears
during the follow-up period | Sum of Morning/Afternoon/Evening Number of drops taken after End of Treatment date.
(from the eCRF form "Frequency of preservative free artificial tears use" forms)  |
| Total number of days of the follow-up period  | Last follow-up available visit* date – End of Treatment date + 1
(* with assessment of Frequency of preservative free artificial tears use)   |
| Time from randomization to study discontinuation (days)   | End of Study date – Randomization date + 1   |
| Primary and Secondary Sjögren's   | For the subgroup analyses, a patient will be classified as primary Sjögren's syndrome if the patient experienced any previous and/or concomitant ocular with diagnosis='Sjogren Syndrome'. Otherwise the patient will be classified as secondary Sjögren's syndrome                |
| Conversion of Time Intervals  | If a time interval was calculated in minutes, hours or days and needs to be converted into months or year the following conversion factors will be used:
• 1 hour = 60 minutes
• 1 day = 24 hours
• 1 week = 7 days
• 1 month = 30.4375 days
• 1 year = 365.25 days |
| General rule  | For calculation of a time interval, in case time is available, it is considered in the formula. Time intervals will be expressed in hours in if less than 24 hours and days if more than 24 hours.   |

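### SAP 9.3 labels artificial-tear use as drops/day but multiplies it by 100, and Table 3 names an eye for the treatment-period count and none for follow-up

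*SAP*

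**What the plan says.** SAP section 9.3 introduces the measure with its unit: "The use (n° drops/day) of preservative free artificial tears will be summarized with descriptive statistics". Summaries are by treatment group, by period (treatment and follow-up) and overall. Two formulas follow, one per period. Each divides total drops by total days and ends in a multiplication by 100. The reader is sent to Table 3 for details.

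Table 3 in SAP section 12.1 defines the components:

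- Treatment-period drops: "Sum of Morning/Afternoon/Evening Number of drops taken for eligible eye between Randomization visit date and End of Treatment date".
- Treatment-period days: "End of Treatment date – Randomization date + 1".
- Follow-up drops: "Sum of Morning/Afternoon/Evening Number of drops taken after End of Treatment date".
- Follow-up days: "Last follow-up available visit* date – End of Treatment date + 1".

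SAP section 3.2.3 and Protocol section 7.1.3 list tear use in each period as an exploratory endpoint and express its frequency in drops/day.

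**The concern.** Two things do not fit together. First, drops divided by days is already drops per day, so the extra factor of 100 contradicts the label. The same factor is correct in the compliance formula of SAP section 9.1, where the result is a percentage. Here the result is a rate. SAP section 7.9, which lists changes from the protocol, mentions no rescaling.

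Second, the two numerators do not follow the same stated rule. One names the eligible eye and the other names no eye. The protocol has patients use the drops in both eyes and record additional drops for each eye (Protocol section 5.1.1), so whether to add the eyes together is a real programming choice.

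At stake are Tables 14.3.2.3.1 and 14.3.2.3.2 and Listing 16.2.5.3. They could show values 100 times the labelled unit, and follow-up values on a different eye basis from treatment-period values.

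**Working it through.** The documents give no numerical result for tear use, so there is no figure to reproduce. The check applies the SAP formulas to a hypothetical patient.

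**Inputs**
- Formulas: SAP section 9.3. Numerators and day counts: SAP Table 3.
- Treatment period: days 1 to 28, so 28 − 1 + 1 = 28 days.
- Follow-up example, cut at the week 12 visit (day 84): drops counted on days 29 to 84, which is 56 days. The Table 3 day count is 84 − 28 + 1 = 57.
- Follow-up use in the example: three drops per eye per day, taken from Protocol section 5.6: "During the 8 weeks of Follow-up period post-treatment one drop will be instilled in both eyes TID".

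**Step 1: the factor of 100 (treatment period, eligible eye)**
- 1 drop/day: 28 / 28 × 100 = 100. Without the factor: 1.
- 2 drops/day: 56 / 28 × 100 = 200. Without the factor: 2.
- 3 drops/day: 84 / 28 × 100 = 300. Without the factor: 3.

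**Step 2: the eye rule (follow-up, three drops per eye per day)**
- Eligible eye only: 3 × 56 = 168 drops; 168 / 57 × 100 = 294.7. Without the factor: 2.95.
- Both eyes summed: 2 × 168 = 336 drops; 336 / 57 × 100 = 589.5. Without the factor: 5.89.

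The ratio of the two readings is 336 / 168 = 2. For the same three drops per eye per day, the treatment period would show 300, and follow-up would show either 294.7 or 589.5.

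**Step 3: the remaining gap between 300 and 294.7**
Follow-up drops are counted after the End of Treatment date, but the day count includes that date. The divisor is therefore 57 where 56 would match the numerator: 168 / 56 = 3.00 against 168 / 57 = 2.95. This is a minor side effect, separate from the two main points.

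**The case against.** The best defence is that little depends on this. The endpoints are exploratory and the summaries descriptive. The factor of 100 is the same constant in both arms, and the printed unit would help a reader recognise the slip. No comparison between periods is a stated endpoint. All of that stands and limits the importance of the point. It does not explain the factor, and SAP section 7.1 does not supply the missing eye rule: it says only that some endpoints use the eligible eye where applicable, with details left to output notes.

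Four stronger readings are tempting, and the documents do not support them.

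- A reader might infer that both eyes are summed in follow-up. Table 3 does not say so; it only omits the eye. The doubling is conditional on how the row is programmed.
- A reader might infer that scheduled drops add a constant three (or six) per day to the follow-up value, hiding as-needed use. The scheduled three-times-daily tears cover only the first eight follow-up weeks, whereas the count can run to week 24. With scheduled drops only, and the last assessment on day 168, the eligible-eye value is 168 / (168 − 28 + 1) = 168 / 141 = 1.19 drops/day before the factor of 100. It is also not certain that scheduled drops enter the count: Protocol section 5.1.1 asks for additional drops to be documented, section 5.6 for use in general, and the diary and eCRF are not among the documents.
- A reader might infer that the SAP must separate as-needed from scheduled drops, or weeks 13 to 24 from earlier weeks. The endpoint is frequency of use and is not defined as a measure of need. Such splits are a reporting preference and may need data fields that the documents do not show.
- A reader might call the summaries meaningless. Within a period the arms are treated alike, so that goes too far.

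**Conclusion.** The point holds, at low severity. The factor of 100 is wrong as written: it reports both exploratory endpoints at 100 times the labelled unit, and this needs no assumption beyond the text of SAP section 9.3. The eye rule is an omission: follow-up values could be up to twice as high for the same behaviour, on the assumption that both eyes are summed and used alike. Until one rule is stated, the two periods and the overall summary, for which section 9.3 gives no formula, are not comparable.

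The factor of 100 cancels from between-arm ratios, although absolute between-arm differences would be scaled up by it. Whichever eye rule is adopted applies to both arms, and it too cancels where patients treat both eyes alike. The co-primary and key secondary analyses are unaffected.

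**What to change.** In SAP section 9.3, delete the multiplication by 100 from both formulas. In SAP Table 3, restrict the follow-up drop count to the eligible eye, so that both periods use the rule already stated for the treatment period. While the row is open, the follow-up day count could be aligned with its numerator, which starts the day after End of Treatment; this is optional.

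The cost is a short SAP text correction and the matching program lines. It needs no new data and changes no primary or key secondary analysis.

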# **10.** Evaluation of Efficacy

# 10.1 Analysis of primary efficacy endpoint

10.1.1 Testing strategy and multiplicity adjustment

The following null hypothesis is defined on the first primary endpoint: the proportion of patients reaching a value of Schirmer I test (without anesthesia) >10mm/5min at week 4 in cenegermin (rhNGF) is lower or equal than control:

H01:  $T_{rhNGF} \leq T_{CONTROL}$ 

H11: TrhNGF > TCONTROL

where  $T_{rhNGF}$  and  $T_{CONTROL}$  are the proportion of patients reaching a value of Schirmer I test (without anesthesia) >10mm/5min at week 4 for cenegermin and control groups, respectively. The null hypothesis  $H_{01}$  will be rejected if the associated primary analysis p-value will be lower than 0.025.

Similarly, the following null hypothesis is defined on the co-primary endpoint: the change from baseline (reduction) in the global SANDE score at week 12 in cenegermin is lower or equal than control:

H02:  $\mu_{rhNGF} \leq \mu_{CONTROL}$ 

H12:  $\mu_{rhNGF} > \mu_{CONTROL}$ 

where  $\mu_{rhNGF}$  and  $\mu_{CONTROL}$  are the change from baseline (reduction) in the global SANDE score at week 12 for cenegermin and control groups, respectively. The null hypothesis H02 will be rejected if the associated primary analysis p-value will be lower than 0.025.

Both null hypotheses  $H_{01}$  and  $H_{02}$  must be rejected to claim superiority of cenegermin over control. Consequently, no multiplicity correction of type I error will be applied on primary endpoints analysis.

